### 1.1. Overview of Device/Procedure

The study objective is to validate STAGE images and, when applicable, their equivalence to conventional MRI through an assessment by a trained certified neuroradiologist in a clinical setting.

The data collected in this study will be utilized to support an FDA 510(k) submission to gain FDA clearance to market the FDA Class II STAGE system in the United States.

*This study does not involve comparing test subjects vs. control subjects, nor does it involve any treatment and follow-up.*

### 1.2. Study Rationale

Several hurdles which radiologists encounter specifically in MRI, are: acquiring the most amount of information; minimizing acquisition time; acquiring images with adequate quality; and standardization of the acquired images. Current neuroimaging protocols are in the realm of 20 minutes which include conventional T1-weighted, T2-weighted, T2 FLAIR imaging and/or Diffusion Weighted Imaging. The image quality depends on several factors including magnetic field strength, coils, image resolution and often differ depending on these factors from scanner to scanner.

The proposed STAGE imaging protocol (Strategically Acquired Gradient Echo) is a multipronged image acquisition and processing approach to address the aforementioned issues. Using specific collection parameters from a 3D gradient echo sequence, MRI scans can be performed for 3/1.5 Tesla magnets across most existing machines, independent of manufacturer. Upon data collection, the images are exported from the PACS archiving system and processed in our STAGE module to generate several weighted contrasts and quantitative maps, then returned to the PACS for radiologic review. All of the contrasts and quantitative maps are co-registered, 3D, and the same image resolution which makes for easy comparison between scans and manufacturers. Having quantitative maps provides source signal which mitigates bias between scanners. This protocol has great potential to decrease scan times, increase hospital and image center throughput, and also provide quality 3D images.

## 2. SUMMARY OF DEVICE DESCRIPTION .....

### 2.1. STAGE

#### 2.1.1.[Device / System Sterile Components]

STAGE is composed of a medical grade computer manufactured by Onyx Healthcare. The system has been tested and certified to ISO standards as well as other compliance standards (see 3.2).

#### 2.1.2.[Device / System Non-Sterile Components]

No non-sterile components exist in the device.

## 3. RISK BENEFIT ANALYSIS .....

### 3.1. Risk Analysis

*The following categories were used to assess the likelihood:*

*"Common" (i.e., approximate incidence > 25%)*

*"Likely" (i.e., approximate incidence of 10-25%)*

*"Infrequent" (i.e., approximate incidence of 1-10%)*

*"Rare" (i.e., approximate incidence < 1%)*

Participation in this study poses a risk for breach of confidentiality. Records will be stored in a safe, lockable storage unit. RARE

MRI may be uncomfortable for some subjects. MRI does not involve the use of radiation; it does however involve the use of a strong magnetic field. Prior to starting the scan each subject will be asked if they have

any metal implanted in their body. The presence of implanted metal will influence the scans. Some subjects who have claustrophobia (fear of small closed places) are concerned about being in the scanner, and if at any point during the scan this concerns the subject, the scanning will be stopped. Some studies, like the MRI, have the potential to cause "peripheral nerve stimulation" (PNS). PNS is a light touching sensation on the skin surface, lasting only for a few seconds and is not harmful to the subject. The MRI machine is operated within federal guidelines so the potential for inducing PNS is low. There is the potential that a magnetic resonance image may reveal an abnormality, such as a cyst or tumor. Many such abnormalities are not clinically significant, but subjects may want to investigate them further. Such a finding may require notifying the subject's primary Physician. RARE

STAGE will use a Medical Grade by Onyx Healthcare, Inc. and may have electrical or power issues. RARE

*What will be done to reduce or monitor these risks?*

- Prospective data will include imaging as well as questionnaire/survey with the neuroradiologist to evaluate the performance of STAGE and its outputs. The study will not consist of retrospective data.
- To minimize the breach of confidentiality risk, the subject's name or hospital number to identify them will not be used on any study records. Instead a unique study number will be assigned to each subject. Only this number will be used on study documents that relate to the subject. The list of subject names and corresponding unique study number will be kept in a secure, locked location. At the end of the project, this list will be destroyed.
- To minimize discomfort during the MRI, pads and blankets will be used to position each subject so they are as comfortable as possible during the scan. Subjects may wear foam earplugs or hearing-protective headphones to reduce hearing the loud noises made by the scanner. Subjects will be able to talk to us throughout the study, and can let us know right away if they want to stop the study and get out of the scanner.

The Onyx High Performance Medical Grade Fanless Box PC (model: MEDPC-9200) which the STAGE software resides has multiple certifications from third parties which conform to safety and quality standards for usage in a clinical environment. The box has certification from:

Presafe: Complies with ISO 13485:2003 requirements

DNV: GL: Complies with ISO 14001:2015, ISO 9001:2015/CNS 12681:2016

Dekra: Complies with FCC CFR Title 47 Part 18: 2016 (subpart C), EN 55011: 2009/A1: 2010 Class B (Group 1), EN 61000-3-2: 2014, En 61000-3-3: 2013, EN 60601-1-2: 2015, IEC 60601-1-2:2014, IEC 61000-4-2 Ed. 2.0: 2008, IEC 61000-4-3 Ed. 3.2: 2010, IEC 61000-4-4, Ed. 3.0: 2012, IEC 61000-4-5 Ed. 3.1: 2014+A1: 2017, IEC 61000-4-6 Ed. 4.0: 2013, IEC 61000-4-8 Ed. 2.0: 2009, IEC 61000-4-11 Ed. 2.1: 2004+A1: 2017.

### 3.2. Justification and Potential Benefit

*To the individual:* There are no benefits for the research subject.

*To society:* Showing that the STAGE protocol has equal to/or better quality than conventional images would have great impact in the clinical realm. Scan times would therefore be reduced, mitigating patient discomfort within the scanner (especially in frail, aged, neurodegenerative subjects, as well as children). The STAGE protocol also an efficient way to collect this many contrasts, and therefore hospitals and imaging centers can increase their throughput. Standardization would also be achieved between manufacturers and field strengths, which allow for ease in longitudinal assessment, repeat scans. Further, standardized data is optimal as input for Artificial Intelligence algorithms for lesion detection, or to discern any abnormalities based on MR signal.

## 4. STUDY OBJECTIVES AND ENDPOINTS .....

### 4.1. Primary Objectives

To evaluate the safety of using the STAGE system in a clinical setting. Potential risks have been mitigated in the User Requirements which will be subject to testing via Verification and Validation.

#### 4.1.1. Secondary Objectives

To evaluate the effectiveness of STAGE output data based on the quality of their image contrasts and maps in comparison with conventional MR images.

### 4.2. Primary Endpoints

4.2.1. Primary Endpoint 1: each STAGE and MRI input or output is graded qualitatively by an experienced individual at the MRI center. Quality grading is performed on a 5-point scale [5=excellent; 4=good; 3=acceptable; 2=poor; 1=unacceptable] on several criteria [blurring/ghosting/ringing; flow artifact; intensity and homogeneity; signal to noise ratio; susceptibility artifacts]. For the questions with a 5-point score, the points will be averaged with scores  $\geq 3$  can be used for clinical diagnosis.

4.2.2. Primary Endpoint 2: contrast appearance will also be graded on a binary basis: passed, failed. All binary questions should have a 'Pass' answer will qualify as "Passed."

### 4.3. Study Success

The study will be considered successful if STAGE data quality is found to be clinically acceptable and generated contrasts are as expected based on statistical testing.

## 5. CLINICAL STUDY DESIGN .....

This is prospective observational, non-interventional cohort study to evaluate the efficacy of the collection protocol and STAGE system processing algorithm. STAGE system output will be compared to the MRI output from the same patient.

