### 8.1. Analysis Samples

The data from up to one hundred twenty (120) subjects will be analyzed. A radiologist will review the quality of the STAGE inputs and outputs as acceptable or not acceptable for clinical review as adjunctive imaging. For each image (STAGE and MRI) input or output, the radiologist will answer survey questions which pertain to the contrast quality and the tissue(s) involved. They will be further compared with output from conventional MR images for quality.

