## 8.3. DATA ANALYSIS AND REPORTING OF RESULTS

### 8.3.1.Analysis of Effectiveness Endpoints

- 8.3.1.1. Primary Endpoint 1: The score of each STAGE and MRI input or output across individuals will be analyzed using a Mann-Whitney tests.
- 8.3.1.2. Primary Endpoint 2: General image quality on a binary basis (passed, failed) will be required to pass in all cases where the input data was found to be clinically useable.

Alpha of  $p < 0.05$  will be considered significant.

## 9. ADVERSE EVENT REPORTING.....

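### Success rests on STAGE images being clinically acceptable, but for the 5-point score section 8 plans only a comparison with MRI and sets no rule against the cut-off of 3

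*Combined protocol and SAP*

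**What the plan says.** Section 4.3 gives the success rule: "The study will be considered successful if STAGE data quality is found to be clinically acceptable". The same sentence adds a condition on the contrasts and closes with a reference to statistical testing. It contains no number and does not mention MRI.

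Section 4.2.1 supplies the scale, "5=excellent; 4=good; 3=acceptable; 2=poor; 1=unacceptable", and the cut-off: "the points will be averaged with scores" of at least 3 that "can be used for clinical diagnosis". It does not say whether the average is taken per image, per output, per subject or over the study.

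Section 8.2 sizes the study on a null hypothesis that STAGE scores no higher than conventional MRI. It uses a paired t-test with a mean difference of 0.5 and a standard deviation of 1.

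Section 8.3.1.1 is the whole analysis of Primary Endpoint 1: "The score of each STAGE and MRI input or output across individuals will be analyzed using a Mann-Whitney tests".

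Two other rules bear on acceptability:
- Section 8.3.1.2 says that the binary grade "will be required to pass in all cases where the input data was found to be clinically useable".
- Section 8.1 says: "A radiologist will review the quality of the STAGE inputs and outputs as acceptable or not acceptable for clinical review as adjunctive imaging". No analysis or required proportion follows.

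**The concern.** The success rule asks an absolute question: are STAGE images good enough? The test named for the graded score asks a relative one: do STAGE and MRI scores differ? A plan can ask both, but this one never says how the first is to be answered from the score.

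The study is meant to support a 510(k) submission (section 1.1). As the plan stands, the unit, the statistic and the pass mark for acceptability would have to be chosen after the scores are in hand. Any claim that section 4.3 was met on the graded score would then rest on a rule that was not prespecified.

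**Working it through.** **1. The plan's own figure.** Inputs from section 8.2: n = 80 pairs, mean difference 0.5, SD 1, two-sided alpha 0.05.
- Noncentrality = 0.5 × √80 / 1 = 4.47.
- Critical value, t with 79 degrees of freedom: 1.990.
- Power from the noncentral t distribution: 99.3%.

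The stated figure of at least 90% therefore holds as a lower bound. The value 3 enters nowhere in it, so it is power for a difference from MRI and not for acceptability.

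**2. The rules side by side.**

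| Section | What is judged | Against what | Decision rule |
|---|---|---|---|
| 4.3 | STAGE quality and contrasts | acceptability; expected contrasts | no number |
| 4.2.1 | averaged 5-point score | 3 | unit and required proportion not given |
| 8.2 | STAGE minus MRI score | 0 | superiority null |
| 8.3.1.1 | STAGE and MRI scores | each other | Mann-Whitney, 0.05 |
| 8.3.1.2 | binary pass/fail grade | pass in every case with usable input | fixed rule |
| 8.1 | acceptable / not acceptable rating | none | none |

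No row in section 8 sets the 5-point score against 3.

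**3. Why the comparison cannot stand in.** The Mann-Whitney statistic counts the pairs in which a STAGE score exceeds an MRI score. Add the same constant to every score and, apart from the ends of the scale, that count does not change. The result therefore carries no information on where STAGE lies relative to 3. For illustration (the documents give no expected means):
- STAGE 2.5, MRI 2.0: difference +0.5, STAGE below 3.
- STAGE 4.0, MRI 4.5: difference −0.5, STAGE well above 3.
- STAGE 4.0, MRI 4.0: difference 0, STAGE well above 3.

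The sign of the difference and the position relative to 3 vary separately.

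**4. What a direct rule would ask at n = 80.** Let k be the number of subjects with an averaged score of 3 or more. The exact (Clopper-Pearson) lower 95% limit is the 0.025 quantile of Beta(k, 80 − k + 1).

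| k/80 | Observed | Lower limit |
|---|---|---|
| 78 | 97.5% | 91.3% |
| 77 | 96.3% | 89.4% |
| 75 | 93.8% | 86.0% |
| 74 | 92.5% | 84.4% |

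A goal of 90% needs at least 78 of 80, and a goal of 85% at least 75 of 80. Both goals are assumptions.

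A rule on the mean is also possible. If one STAGE score has SD 1 (assumed, because the SD of 1 in section 8.2 belongs to the difference), the observed mean must exceed 3 + 1.990 × 1/√80 = 3.22.

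**5. The existing absolute rule.** If each case passes the binary grade with probability 0.99 independently, all 80 pass with probability 0.99^80 = 0.45. How this rule combines with a rule on the score therefore matters.

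**The case against.** - **The plan already has an absolute rule.** Section 8.3.1.2 does not depend on MRI and calls its subject general image quality. This stands, and it would be wrong to say that the plan contains only relative comparisons. But section 4.2.2 describes the same endpoint as contrast appearance, and the rule uses neither the 5-point score nor the cut-off of 3.
- **Section 4.3 may not promise a test of acceptability.** Its closing words on statistical testing can be read as applying to the contrasts only. Acceptability could then be checked descriptively against 3. This reading is open, but a descriptive check still needs a unit and a pass mark, and neither is given.
- **The comparison with MRI is a legitimate aim.** Section 4.1.1 makes it a secondary objective. That is a reason to keep it, not a reason to let it answer section 4.3.

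A reader might go further and infer that the plan would deliver a wrong verdict in both directions, and nearly always. The documents do not support that. Section 4.3 does not say that a significant Mann-Whitney result means success or that scoring below MRI means failure, so no wrong verdict follows from the text. The 99.3% in the working belongs to the paired t-test used for sizing. With the SD of the difference held at 1 and a difference of 0.5, simulated power of the named Mann-Whitney test at n = 80 is about 99%, 94% and 76% for assumed within-subject correlations of 0, 0.5 and 0.7. The documents give no correlation.

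**Conclusion.** The concern holds as a missing link. Success in section 4.3 includes clinical acceptability, section 4.2.1 gives it a numeric meaning, and nothing planned for that score in section 8 refers to the number. Carrying out section 8 exactly as written would leave the acceptability part of success undecided on the graded score.

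This rests on two readings: that acceptability in 4.3 means the cut-off in 4.2.1, which is the only numeric definition available, and that the binary rule in 8.3.1.2 is a separate endpoint, as 4.2.2 presents it. The documents do not show how often, or in which direction, a conclusion would be wrong. The thresholds of 78 and 75 out of 80 indicate scale only and depend on the assumed goals and on 80 evaluable subjects.

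**What to change.** In sections 4.3 and 8.3.1.1:
1. Define acceptability per subject and per STAGE output as an averaged 5-point score of 3 or more, and state what the average is taken over.
2. For each STAGE output, estimate the proportion of evaluable subjects who meet this, with an exact 95% confidence interval.
3. Count the acceptability part of 4.3 as met when the lower limit exceeds a goal that is justified and fixed before scores are seen.
4. State whether every STAGE output must meet the goal (section 7.2 lists eleven entries) or only a named subset.
5. State how this rule combines with the all-pass rule in 8.3.1.2, and what role the rating in 8.1 plays.
6. Report the STAGE-MRI comparison as a separate result, analysed as paired in line with section 8.2.

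A one-sample bound on the mean score against 3 would also fit the averaging language of 4.2.1. The proportion says more directly how many subjects have usable images.

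The cost is an amendment to the success criterion as well as to the analysis text, and one goal that must be justified. No new data are needed, since the scores are already to be collected. The downside for the sponsor is that success becomes explicit and can be failed, more easily so if every output must pass.

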### 5.1. Test Arm

n/a.

### 5.2. Control Arm

n/a

## 6. SUBJECT SELECTION

### 6.1. Subject Inclusion Criteria

- Subjects 6-80 years of age, inclusive.
- Literate in English
- No contraindications to MR\*
- Not claustrophobic

\* ACR Guidance Document on MR Safe Practices 2013 J Magn Reson Imaging 2013 Mar;37(3):501-530

### 6.2. Subject Exclusion Criteria

[figure not shown]
- Subject has diffuse white matter disease or leukoaraiosis.
- Participants, or Subject's parent or guardian unable to read and sign an informed consent.
- Women who are pregnant or breast-feeding.
- Those with major surgery within the past eight weeks or scheduled surgery within 30 days.
- Chronic back pain or inability to lie still for 5 minutes or more.
- History of drug or alcohol abuse.
- Individuals who exceed 38 BMI or 320 lbs.
- Individual whose girth exceeds the magnetic bore.
- Direct employee or student of the PI.
- Participants belong to a vulnerable group.

### 6.3. [Procedure] Eligibility Criteria

All subjects who meet all inclusion and do not meet any exclusion criteria are eligible to participate in the study. Subjects who are eligible will not be compensated for this study.

## 7. STUDY PROCEDURE

### 7.1. Study Diagram

### 7.2. Clinical Procedure for STAGE

### **System setup\***

\*This study assumes the principal investigators and MRI staff have adequate understanding of the MRI sequences involved as well as quantitative mapping involved.

Per user requirements and manual, the STAGE module will be installed by a trained technician from SpinTech, Inc. Tests will be performed to ensure networking setup is successful in which the module is connected to PACS system, with the ability to receive and send data.

The subject will undergo a survey administered by a Physician to determine he/she is cognitively-intact, and meets all of the inclusion criteria and none of the exclusion criteria.

#### **MRI Scan**

Total study time which includes the patient intake and the scans may take up to two hours.

The subject will undergo a brain MRI scan using the STAGE Protocol\* either at 3 Tesla or 1.5 Tesla field strength. The STAGE protocol consists of two flow-compensated spoiled 3D gradient-echo multi-echo scans, run at different specific flip angles.

For 3T\*\* scan parameters are as follows: FOV: 256x192 mm, matrix size: 384x288 or 384x384, slices:  $\geq 64$ , slice thickness: 1.34mm and 2mm, TE= 7.5/12.5/17.5ms, bandwidth per pixel <240Hz, and TR=25ms. Two multi echo scans will be run: with FA = 6° and one with FA = 24°. Data will be collected with In-plane resolutions of 0.67x1.33mm and 0.67x1mm (freq dir x phase dir). Scanner options for partial fourier and elliptical sampling should be turned on if available. The total protocol time will be roughly 5 minutes.

For 1.5T\*\*, the scan parameters are: FOV: 256x192 mm, matrix size: 384x288 or 384x384, slices:  $\geq 48$ , slice thickness 2.7mm and 2mm, TE= 10/20/35ms, bandwidth per pixel <200Hz, and TR = 40ms. Data will be collected with in-plane resolutions of 0.67x1.33mm and 0.67x1mm (freq dir x phase dir). Two multi echo scans will be run: One with with FA of 7° and one with 35°.

Upon collection, the subject's raw DICOM files transferred to the PACS system and then manually sent by the user to the STAGE module for post-processing. (*note: the subject need not be present for this step*) The processed STAGE images will be sent back to the PACS system where they remain within the participant's scan folder and are clearly labeled. They can then be viewed at an integrated workstation. Original and temporary data linked to the patient will be deleted from the module after it is processed.

The generated contrasts are the following:

- Enhanced T1-weighted images (T1We)
- Susceptibility Weighted Images (SWI)
- T1 Maps
- Proton Density Maps
- R2\* Maps
- Susceptibility maps (SWIM)
- Pseudo and modified pseudo SWIM
- True SWI (tSWI)
- Dual inversion recovery images of the CSF, White matter, and Gray matter
- MRA
- Maximum or minimum intensity projections of SWI, tSWI, R2\*

Options for outputting sagittal and coronal reformatted images will be provided for the T1We and T1 maps. Additionally, all images will have an option for skull stripping as well as a 1x1x2 sliding window filter.

\*No contrast administration is required in this protocol.

\*\* These parameters may vary slightly depending on the limitations of the scanner software version.

For the purposes of validation, additional data will be collected as a gold standard to compare with the STAGE inputs outputs. This includes 3D T1 MP-RAGE and proton density weighted imaging, which are to be collected at recommended parameters, but with similar FOV and matrix size to the images in the STAGE imaging protocol. Scan collection times will range from about 5 – 10 minutes, depending on the field strength.

The MD will be given a survey with questions concerning image quality, whether contrasts based on the tissue properties match the input and outputs, or if anatomical structures appear or not.

No biological specimens will be collected in this study. The study involves MR imaging. STAGE involves an Investigational medical device which is labeled for Investigational Use Only, per FDA IDE labeling requirements/research purposes only.

For children (subjects aged 6-17 years) involved in this study, headphones will be provided to ensure comfort. The subject may need to stay still for a time period up to 40 minutes. A sedative may be prescribed by the subject's primary physician to be taken prior to the scan to mitigate motion during the scan. This study will not involve any intravenous sedation. The subject will be informed that he or she can rest shortly between sequences (each sequence may last 5-10 minutes) if needed, and that the study can be stopped at any time if he or she needs.

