### 12.2. Records

Records and scan data will be protected in a locked-storage unit within a locked office.

## 13. APPENICES .....

n/a

## 14. TABLES AND FIGURES .....

FIGURE 1: STAGE Design / Schema

[figure not shown]

Figure 1: MRI images will be collected from scanners which will already be FDA-approved. The data collected will be de-identified with no information able to be traced back to the subject. Then the data will be sent to Picture Archiving and Communications System. From there, the raw DICOM will be sent to a node on the processing module in which it is sorted and read, then processed using the STAGE algorithms to generate the images listed in Section 7.2. Then the data are sent back to the PACS for the radiologist to review at his/her workstation.

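### The plan describes no masking to image source, random reading order or separation from labelled questions for Endpoint 1's STAGE and MRI quality grades, so reader expectation could shift that comparison either way.

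*Combined protocol and SAP*

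**What the plan says.** **The grade.** Section 4.2.1 has an experienced person at the MRI centre grade each STAGE and MRI input or output: "Quality grading is performed on a 5-point scale", on criteria such as artefact, homogeneity and signal to noise. Scores are averaged, and 3 or more counts as usable for diagnosis.

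**The comparison.** Section 5: "STAGE system output will be compared to the MRI output from the same patient". Section 4.1.1 makes image quality "in comparison with conventional MR images" a secondary objective. Section 8.2 nevertheless sizes the study on rejecting the null that STAGE scores are no higher than MRI scores, and Section 8.3.1.1 tests the scores under Primary Endpoint 1 with a Mann-Whitney test. Success in Section 4.3 requires that "STAGE data quality is found to be clinically acceptable" and that contrasts are as expected, with reference to statistical testing.

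**The reading route.** Under MRI Scan in Section 7.2, processed STAGE images return to PACS, where they stay in the participant's "scan folder and are clearly labeled". The legend of Figure 1 (Section 14) says the data are "sent back to the PACS for the radiologist to review at his/her workstation".

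**The survey.** Section 7.2 gives the MD a "survey with questions concerning image quality, whether contrasts based on the tissue properties match the input and outputs". Section 8.1 has a radiologist answer survey questions for each STAGE and MRI image.

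**The comparators.** Section 7.2 describes gold-standard scans: "This includes 3D T1 MP-RAGE and proton density weighted imaging".

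No available section mentions masking to image source, reading order, separate sessions or removal of labels. The de-identification in Section 3.1 and the Figure 1 legend hides who the subject is, not which method made the image.

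**The concern.** A 5-point grade of blurring, artefact or homogeneity is a judgement. A grader who knows which image comes from the new system can be swayed by that knowledge. The direction is open: Section 3.2 hopes to show STAGE equal or better, while Section 7.2 calls the conventional scans the gold standard.

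The described route makes the source visible. The survey adds to this, because judging whether contrasts match between inputs and outputs requires knowing what each image is, and nothing keeps that question apart from quality grading.

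What is at stake is the STAGE-versus-MRI comparison. Although worded as a secondary objective, it is what the study is sized on and the only comparison for which a test is named. The assumed effect is 0.5 points, so a shift of a few tenths is a large part of it. Once the reads are done, no analysis can separate such a shift from a real difference. The absolute criterion, an average of 3 or more, is affected only for images scoring near 3.

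**Working it through.** **1. The plan's own figure.** Inputs from Section 8.2: n = 80 pairs, mean difference 0.5, SD of the difference 1, two-sided alpha 0.05, paired t-test. The noncentrality is 0.5/1 × √80 = 4.47 with 79 degrees of freedom. Power is 99.3%, which agrees with the stated minimum of 90%. At n = 80 the paired test has 90% power for a difference of about 0.37, so it is sensitive to shifts of a few tenths from any cause.

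**2. Adding a reader shift.** Let b be the average shift toward STAGE caused by knowing the source. The expected observed difference is then the true difference plus b. The documents give no value for b, so 0.1, 0.2 and 0.25 points are assumed. With no true difference, the chance that the paired t-test shows a significant STAGE advantage (upper tail, 2.5%) comes from the same noncentral t with noncentrality b × √80:

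- b = 0: 2.5%
- b = 0.1: 14.1%
- b = 0.2: 42.4%
- b = 0.25: 59.8%

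**3. The same with the planned Mann-Whitney test.** This test ignores the pairing, so the answer also depends on the correlation between a subject's two scores, which the documents do not give. With the SD of the difference fixed at 1 and correlation ρ, each score has SD 1/√(2(1 − ρ)): 0.71, 0.85, 1.00 and 1.29 for ρ = 0, 0.3, 0.5 and 0.7. Simulation used continuous normal scores, one score per subject and modality, and 40,000 runs per cell. The table gives the chance of a significant STAGE advantage.

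| Observed mean difference | ρ = 0 | ρ = 0.3 | ρ = 0.5 | ρ = 0.7 |
|---|---|---|---|---|
| 0 | 2.5% | 1.1% | 0.4% | 0.1% |
| 0.1 | 13.5% | 7.4% | 3.2% | 0.5% |
| 0.2 | 40.8% | 27.2% | 16.1% | 4.0% |
| 0.25 | 58.3% | 42.9% | 28.1% | 9.2% |
| 0.5 | 99.1% | 97.5% | 93.7% | 76.4% |

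With no true difference, the rows 0.1 to 0.25 are false STAGE advantages produced by the shift alone.

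**4. The other direction.** If the true difference is the planned 0.5 and expectation takes 0.25 away from STAGE, the observed difference is 0.5 − 0.25 = 0.25. Mann-Whitney power then falls from the last row to the row above it: from 99% to 58% at ρ = 0, and from 76% to 9% at ρ = 0.7.

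**5. Bounded scores.** Scores in steps of 0.2, limited to 1–5 with an assumed mean of 3.5, give 42%, 28%, 17% and 6% for a 0.2 shift at the four correlations. These are close to the table.

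**The case against.** - **The labelling sentence concerns PACS storage, not scoring.** A reader might infer that the plan prescribes an unmasked read. It does not: labelling returned images is sensible practice, and the scoring session is not described. What stands is that no other route is described and nothing says the labels are hidden for grading. The study diagram and the image of Figure 1 are not shown in the text read, so the point covers the available text only.
- **The cited reader may not be the grader.** Section 4.2.1 names an experienced person at the MRI centre; Sections 7.2 and 8.1 and Figure 1 name an MD or radiologist. If they differ, the argument that the contrast-match question reveals the source to the quality grader weakens. The documents do not settle this, and they mask neither person.
- **The consequence is limited.** Success in Section 4.3 rests on acceptable quality and expected contrasts, and the comparison is a secondary objective. A reader might take the percentages above as the chance of wrongly declaring the study successful. They are not. But Section 4.3 also refers to statistical testing, and the only test named is the STAGE-versus-MRI one, so the comparison cannot be set aside.
- **The size rests on assumptions.** This is right. Much of the spread across correlations comes from using an unpaired test on paired scores, which is a separate matter. Same-subject scores may well be correlated, which would point to the lower Mann-Whitney figures.
- **Masking may not work fully.** Only two comparators are named, and a trained reader may recognise the contrast in both pairs. That limits the benefit of removing labels. Random order and early locking of the scores remain feasible regardless.

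**Conclusion.** The omission is real. As written, the plan leaves the subjective STAGE-versus-MRI comparison open to reader expectation in either direction, and its effect could not be separated from a true quality difference.

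The size is illustrative only. For an assumed 0.2-point shift toward STAGE with no true difference, the chance of a significant STAGE advantage is about 4% to 41% with the Mann-Whitney test (correlation 0.7 to 0) and 42% with the paired t-test. The shift, the correlation and the use of one score per subject and modality are all assumptions; 80 pairs and SD 1 come from Section 8.2.

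The documents do not support saying that the read is known to be unmasked, that the bias must favour STAGE, or that the study would probably succeed falsely. This is a change the sponsor should make because it is cheap and the problem cannot be repaired after reading. Confidence is medium, since the scoring session and the identity of the grader are not described.

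**What to change.** In Sections 4.2.1, 7.2 and 8.1, state who gives the Endpoint 1 grade and add these rules for that person:

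1. Present all images under coded names in random order, with one subject's STAGE and MRI images not read back to back.
2. Remove STAGE and device labels and overlays from outputs that have a conventional comparator: enhanced T1-weighted images with MP-RAGE, the proton density map with proton-density-weighted images, and any other comparator collected.
3. Lock the quality scores before the labelled Endpoint 2 and contrast-match questions are answered.
4. Keep the PACS labels for the clinical workflow. State that outputs without a comparator are scored unmasked, and that masking may be incomplete where the contrast is recognisable, possibly for both named pairs.

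If such a read is already intended, it only needs to be written down.

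**Cost.** Existing study staff other than the grader must code the images, strip labels, prepare the reading list and hold the key, possibly at several sites (Section 8.2.1 allows more than one). Some reading time is added. No extra reader, scan or subject is needed, and the sample size does not change. Only part of the bias is removed.
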